18.4 Data monitoring committee

No data monitoring committee has been planned for this study.

18.5 Amendments to the Protocol

Modifications of the signed protocol are only possible by protocol amendments with the agreement of all responsible persons.

The investigator should not implement any deviation from, or changes to the protocol without agreement by Alfasigma S.p.A. and prior review and documented approval/favourable opinion from the IRB/IEC of an amendment, except where necessary to eliminate an immediate hazard(s) to trial subjects, or when the change(s) involves only logistical or administrative aspects of the trial.

Protocol amendments must be submitted to the appropriate regulatory authorities.

Alfasigma S.p.A. and the Investigator/Institution must have approval/favourable opinion from the IRB/IEC for any amendment to the protocol.

Any protocol amendment must be distributed to those who received the original protocol and be appended to it.

18.6 Closure or Discontinuation of Study and Site

Upon completion of the study, the following activities, when applicable, must be conducted by the monitor in conjunction with the Investigator, as appropriate:

- Return of all study data to the Sponsor or its designee
- Data clarifications and/or resolutions
- Accounting, reconciliation, and final disposition of used and unused study drug
- Review of site study records for completeness.

18.7 **Premature Discontinuation of the Study in a Trial Site**

The study site can be discontinued at the request of the Sponsor, the Investigator, or regulatory authorities.

Conditions that may warrant discontinuation of the study site include, but are not limited to the following:

• The centre cannot include an adequate number of subjects within the planned time.

- Serious and/or persistent non-compliance with the protocol.
- Careless or premeditated false documentation in the CRFs.
- Inadequate co-operation with the Sponsor.
- Non-compliance with GCP, SOPs or regulatory requirements.
- The investigator asks to discontinue the trial.
- The submission of knowingly false information from the research facility to regulatory authorities

If the trial is prematurely terminated or suspended for any reason, the subjects will be informed promptly, appropriate therapy and follow-up will be assured and where required the relevant regulatory authorities will be informed. The IRB/IEC will be promptly informed and provided with a detailed written explanation.

18.8 **Premature Discontinuation of the Whole Study**

If the trial is prematurely ended or suspended, Alfasigma S.p.A. will promptly inform the Investigators/Institutions, and the regulatory authorities with appropriate justifications. A written explanation will be promptly sent to the IRB/IEC by Alfasigma S.p.A. or the Investigator/Institution, as specified in the regulatory requirements.

18.9 Insurance for Subjects

Alfasigma S.p.A will arrange insurance for all study subjects. The following guidelines must be taken into account:

- Any serious adverse event which may be correlated or not to investigational product or diagnostic procedures during the trial must be reported to the sponsor or the CRO immediately.
- The insurance company is entitled to ask all doctors involved in the treatment of a subject, other insurance companies and the national insurance for information which might help to clarify the cause of injury. Before enrolment in the study a subject must be informed of insurance against trial-related injuries and who to contact for compensation.

The terms of the insurance will be included in the Investigator's Study File.

18.10 Disclosure of all Information and Results

By signing the study protocol, the investigator agrees to keep confidential all information and results concerning the study and the investigational product, until the data are published.

18.11 **Publication policy**

The Sponsor declare its intent to publish the results of the study, after completion of the regulatory Report.

The personal data especially sensitive data regarding the clinical trial, will be only dissemination in strictly anonymous form.

The Sponsor will work with the protocol development team and will identify a lead author for the manuscript development. The authors for the manuscript will be determined by the amount of effort and participation each Investigator contributes towards the study design, the study conduct, as well as the analysis of study results.

All of the parties agree to provide the other with the text sufficiently in advance to allow examination,

prior to submission to a scientific journal.

It is understood by the Investigator that the information developed in the clinical study may be disclosed, as required, to other clinical Investigators, and regulatory authorities.

18.12 Ownership

All data and records provided by the Sponsor or generated during the study (other than a subject's medical records) and all inventions discovered in the course of conducting the study are the property of the Sponsor. If a written contract for the conduct of the study which includes ownership provisions inconsistent with this statement is executed than contract's ownership provisions shall apply rather than this statement.

18.13 Contracts, Finances

In addition to the protocol trial-related duties, functions and financial aspects must be specified in a separate contract between Alfasigma S.p.A., the investigator and any other parties involved in the clinical trial.

19. **REPORTING**

After completion of the study an "integrated" full report will be prepared (according to the ICH Harmonised Tripartite Guideline Topic E3 "Structure and Content of Clinical Study Reports.

CRF	Case Report Form
CS	Clinically Significant
CSR	Clinical Study Report
DLQI	Dermatology Life Quality Index
eCRF	Electronic Case Report Form
EIR	Extended Intestinal Release
EMA	European Medicines Agency
FAS	Full Analysis Set
FDA	Food and Drug Administration
H ₂	Hydrogen
HPLC-MS/MS	High-Performance Liquid Chromatograph Triple Quadrupole Mass Spectrometer
IBS-SSS	Irritable Bowel Syndrome - Symptom Severity Scale
ICH	International Conference on Harmonisation
IGA	Investigator's Global Assessment
IQR	Interquartile Range
IRT	Interactive Response Technology
kg	Kilogram
L-BT	Lactulose Breath Test
LOCF	Last Observation Carried Forward

LS	Least Squares
m	Meter
MedDRA	Medical Dictionary for Regulatory Activities
mg	Milligram
mmHg	Millimeters of Mercury
PK	Pharmacokinetic
PP	Per Protocol Analysis
PT	Preferred Term
SAE	Serious Adverse Event
SAF	Safety Analysis Set
SAP	Statistical Analysis Plan
SD	Standard Deviation
SOC	System Organ Class
TEAE	Treatment Emergent Adverse Event
TID	Three Times Daily
TLFs	Tables, Listings, and Figures
US	United States
V1	Screening Visit
V2	Randomization/Baseline Visit
V3	End of Treatment Visit
V4	End of Study Visit
VAS	Visual Analogue Scale
WHO-DD	World Health Organization Drug Dictionary

2 Introduction

This statistical analysis plan (SAP) describes the planned statistical analysis and reporting of the clinical study protocol titled "A phase IIa, multicenter, double blind, placebo controlled, randomized clinical trial to assess safety, efficacy and pharmacokinetics of Rifaximin Delayed-Release (Rifaximin-EIR) in patients with moderate-to-severe papulopustular rosacea" version 2.0, dated on March 25, 2022.

The structure and content of this SAP provides sufficient detail to meet the requirements identified by the US Food and Drug Administration (FDA), European Medicines Agency (EMA), and International Conference on Harmonisation (ICH) of Technical Requirements for Registration of Pharmaceuticals for Human Use: Guidance on Statistical Principles in Clinical Trials [1]. All work planned and reported for this SAP will follow internationally accepted guidelines, published by the American Statistical Association [2] and the Royal Statistical Society [3], for statistical practice.

The purposes of this SAP are to:

- Outline the types of analyses and presentations of data that will form the basis for drawing conclusions to the study objectives and hypotheses outlined in the protocol
- Explain in detail how the data will be handled and analyzed, adhering to commonly accepted standards and practices for Good Statistical Practice

All analyses described in this plan are considered a priori analyses in that they have been defined prior to locking the study database and unblinding. The planned analyses identified in this SAP will be included in clinical study reports (CSRs) and may be included in regulatory submissions, or future manuscripts. Also, post-hoc exploratory analyses not identified in this SAP may be performed to further examine study data. Any post-hoc or unplanned exploratory analyses performed will be clearly identified as such in the final CSR.

The following documents were reviewed in preparation of this SAP:

- Protocol version 2.0 issued on March 25, 2022:
 - RE-ROS2002-2021_Study_Protocol_Version_2.0_25Mar2022 (signed by Sponsor)
 .pdf
- Electronic Case Report Forms (eCRF):
 - eCOS UniqueCRFs RE-ROS2002-2021 2021-12-06 15 18 37.pdf
- ICH Guidance on Statistical Principles for Clinical Trials (E9)

The reader of this SAP is encouraged to also read the clinical study protocol and other identified documents for details on the planned conduct of this study. Operational aspects related to collection and timing of planned clinical assessments are not repeated in this SAP unless relevant to the planned analyses.

Any changes to the protocol or eCRF may necessitate updates to the SAP. In case of deviations from this SAP, explanations will be provided in the CSR for minor updates and in an SAP amendment for major updates.

3 Study Objectives and Endpoints

3.1 Study Objectives

- 1. To evaluate the safety and the efficacy of two different doses of Rifaximin-EIR 250 mg tablets (250 mg TID and 500 mg TID), administered for 30 days in subjects with moderate-to-severe papulopustular rosacea
- 2. To evaluate the pharmacokinetics of these two doses of Rifaximin-EIR in a sub-group of subjects

3.2 Study Endpoints

3.2.1 Co-primary efficacy endpoints

The following co-primary efficacy endpoints will be clinically assessed by the Investigator:

- 1. Change from baseline in number of rosacea inflammatory lesions (papules and pustules) at the end of treatment (Day 30)
- Percent of subjects showing treatment success, defined as an IGA score of 0 (clear) or 1 (almost clear), with at least a 2-grade improvement from baseline to the end of treatment (Day 30).

Success of the study will be declared in any of the active treatment groups if both the co-primary efficacy endpoints will be satisfied (note: the two items may not necessarily occur in the same patient).

Table 1. Investigator's Global Assessment (IGA) Score

Grade	Description	Amount and size of inflammatory lesions present
0	Clear	None
1	Almost Clear	Very few, small papules /pustules
2	Mild	Few small papules/pustules
3	Moderate	Several small or large papules/pustules
4	Severe	Numerous small and/or large papules/pustules

3.2.2 Secondary Efficacy Endpoints

- 1. Mean change from baseline in number of inflammatory lesions (papules and pustules) at end of study (Day 60).
- 2. Percent of participants showing treatment success (i.e. IGA score of 0 or 1) at end of treatment (Day 30) and/or end of study (Day 60).
- 3. Percent of participants with IGA score of 0 (clear) at end of treatment (Day 30) and/or end of study (Day 60).
- 4. Change from baseline in the following rosacea additional features at end of treatment (Day 30) and/or end of study (Day 60):
 - pain, burning/stinging and itching (measured using a 0-10 cm Visual Analogue Scale (VAS));
 - telangiectasia (absent=0, mild=1, moderate=2, severe=3);
 - ocular manifestations (absent=0, mild=1, moderate=2, severe=3);
 - phymatous changes (absent=0, mild=1, moderate=2, severe=3).
- 5. Change from baseline in facial non-transient erythema (absent=0, mild=1, moderate=2, severe=3) at end of treatment (Day 30) and/or end of study (Day 60).
- 6. Change from baseline in abdominal pain score at end of treatment (Day 30) and/or end of study (Day 60).
- 7. Change from baseline in abdominal distension score at end of treatment (Day 30) and/or end of study (Day 60).

- 8. Change from baseline in bowel habit satisfaction score at end of treatment (Day 30) and/or end of study (Day 60).
- 9. Change from baseline in global severity of abdominal symptoms score at end of treatment (Day 30) and/or end of study (Day 60).
- 10. Percent of participants showing treatment success according to a Modified IGA scale (i.e. score of 0 or 1) including erythema but excluding rosacea inflammatory lesions at end of treatment (Day 30) and/or end of study (Day 60).
- 11. Percent of participant showing treatment success according to a Modified IGA scale (i.e. score of 0 or 1) including erythema and rosacea inflammatory lesions at end of treatment (Day 30) and end of study (Day 60).

3.2.3 Pharmacokinetic Assessments

Pharmacokinetics of the single dose (i.e. at Day 1 after the first dose administration) and the repeated doses (i.e. at Day 30 after the last dose) will be assessed on the PK sub-study population.

PK parameters to be calculated/estimated according to a non-compartmental approach (NCA) are detailed in Section 9.

3.2.4 Safety Assessments

Safety assessments will include:

- Complete physical examination
- Vital signs (including heart rate, blood pressure, and body temperature) and height, weight and BMI
- Routine laboratory parameters (haematology, biochemistry, urinalysis)
- Adverse events (AEs)
- Withdraw of subjects from study due to adverse events

4 Study Overview

4.1 General Study Design and Plan

Subjects will be offered participation to the PK sub-study. If they agree, and have a suitable PK profile, they will be randomized according to the relevant stratum; otherwise, they will enter the main study.

Subjects will be dispensed blinded investigational product according to the randomization schedule. Investigational product will be dispensed at the Day 1 (Randomization) visit; at this visit, each eligible subject will receive a patient's kit containing two "treatment bottles", covering the treatment necessary for 30 days of study. All tablets are identical in appearance and the strengths are placebo and 250 mg. Subjects will be instructed to take 2 tablets of investigational product three times daily (TID) by mouth, in order to maintain study blinding. For the 250 mg TID dose groups this comprises one active and one placebo tablet. For the 500 mg TID dose group, this comprises two 250 mg tablets. For the placebo dose group, this comprises two placebo tablets. TID doses of the assigned treatment will be administered from Day 1 to Day 29. On Day 30 just the first daily dose will be administered.

There will be 3 study drug treatment arms:

- Two tablets of Rifaximin-EIR 250 mg formulation TID (1500 mg daily) for 29 days; on Day 30 subjects will receive two tablets of Rifaximin-EIR 250 mg in single administration (500 mg).
- One tablet of Rifaximin-EIR 250 mg formulation TID (750 mg daily) + one tablet of placebo TID for 29 days; on Day 30 subjects will receive one tablet of Rifaximin-EIR 250 mg and one tablet of placebo in single administration (250 mg).
- Two tablets of placebo TID for 29 days; on Day 30 subjects will receive two tablets of placebo in single administration.

For subjects included in the PK sub-study the first drug intake must be performed at the investigational site in occasion of the randomization visit (Day 1), immediately after the first blood draw (for PK analysis) and preferably early in the morning (approximately 8:00 a.m.). Also, at Day 30 subjects participating in the PK sub-study will stay overnight at the center to complete the PK procedures.

4.2 Inclusion-Exclusion Criteria

Inclusion and exclusion criteria can be found in Section 9.2 and 9.3 of the study protocol.

4.3 Subject Randomization

Randomization will be carried out using an interactive response technology (IRT) system, with central randomization following a 1:1:1 ratio between the 3 treatment arms, based on a block randomization method. Randomization will be stratified by the following factor:

- L-BT status H₂ ≤ 10 ppm
- L-BT status H₂ > 10 ppm

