	delayed release formulation of Rifaximin that contains enteric-coated
	microgranules of Rifaximin.
	I ne new formulation used in this trial, Rifaximin-EIR 250mg tablet (not
	intestinal concentration and therapeutic effect
Rationale and	Rosacea is a common chronic inflammatory relapsing-remitting skin
Objectives:	condition almost exclusively affecting the central area of the face and
	the eyes.
	Based on its main clinical manifestations rosacea has been classically
	divided into the following four subtypes: i) erythematotelangectic, ii)
	papulopustular, iii) phymatous, and iv) ocular. Recent modifications of
	international clinical guidelines however have focused on individual
	features rather than combination of features. This contemporary
	independently diagnostic (persistent central facial erythema and phyma), and other major features that are diagnostic when in combination (i.e. papules and pustules, facial telangiectasia excluding alar involvement, transient central facial erythema, otherwise known as flushing, and specific ocular manifestations). Preliminary evidence suggests that treatment with rifaximin, a poorly absorbed oral antibiotic drug may be beneficial in patients with rosacea, specifically in those with papulopustular phenotype.
	The objective of this study is twofold:
	 to explore the safety and efficacy of two doses of oral Rifaximin delayed-release (750mg/day and 1500mg/day) administered t.i.d. for 30 days versus placebo in adults with moderate-to-severe papulopustular rosacea. in a sub-group of patients, to assess the pharmacokinetics (PK) of the 750mg/daily and 1500mg daily dose of Rifaximin- EIR 250mg administered using a t i d schedule
Phase	Ila
Evening and al	This is Proof of Concept phase lie multiconter double blind
design:	placebo-controlled, randomized clinical trial.

T tr m sı sı	wo hundred one (201) eligible subjects are planned to participate in ne main study while a subgroup of 18-36 (a minimum of 6 and a naximum of 12 subjects per arm) are planned to participate in the PK ub-study. Patients participating in the PK study will be randomly elected from the whole population.
A a o C	At randomization visit, subjects will be 1:1:1 randomized to receiving ny of the two daily doses of active treatment or placebo. TID doses of the assigned treatment will be administered from Day 1 to Day 30. On Day 30, just the first daily dose will be administered.

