10.3 Method of Assigning Subjects to Treatment Groups / Randomisation

A unique subject's identification number will be assigned to all subjects consenting to be enrolled in the study obtained concatenating the center number with the screening number.

A subject who fails to meet the protocol eligibility criteria will be identified as screening failure; his/her identification number will not be reallocated.

Randomisation will occur at visit V2 after all baseline procedures have been performed and eligibility for the study has been confirmed.

Participants will be randomised, on a 1:1:1 basis, to Rifaximin-EIR 250 mg three times a day (750 mg daily) for 29 consecutive days and Rifaximin-EIR 250 mg single dose on Day 30, Rifaximin-EIR 500 mg three times a day (1500 mg daily) for 29 consecutive days and Rifaximin-EIR 500 mg single dose on Day 30, or placebo for 30 consecutive days.

Blocks will be used to assure treatment balance.

Patients will be stratified at randomization based on their L-BT status (negative vs. positive) and PK sub-study participation (yes or not).

Randomization will occur throughout an IWR system integrated into the e-CRF.

At V2, the randomization system will assign an individual Patient's kit number based on a pre-defined randomisation list.

The enrolment will be competitive.

Decoding of randomization in case of emergency is described in chapter 11.4.

The subjects will be offered participation to the PK sub-study. If they agree, they will be randomized according to the relevant stratum maintaining treatment balance among groups; otherwise, they will enter the main study.

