16. STATISTICAL PLAN AND DETERMINATION OF SAMPLE SIZE

The following describes the statistical analysis as it is at the time of planning the trial. A detailed Statistical Analysis Plan (SAP) will be issued after the study starts.

SAS software (V.9.3 or subsequent) will be used for all statistical analyses.

The primary objective of the study is to evaluate the effect of Rifaximin Delayed-Release 500 mg t.i.d. or Rifaximin-EIR 250 mg t.i.d. vs placebo in terms of

- absolute change from baseline in number of rosacea lesions (papules and pustules) at the end of treatment (V3, Day 30), and
- rate of subjects showing treatment success defined as an IGA score of 0 (clear) or 1 (almost clear) with at least a 2-grade improvement from baseline, at the end of treatment (V3, Day 30).

Due to the Proof of Concept purpose of this trial, no alpha-level adjustment for multiplicity will be applied.

A unique randomization list will be created. The randomization list will be stratified by L-BT status (negative vs positive) and by PK sub-study participation (yes or not).

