16.1 Determination of Sample Size

The sample size estimation is based on the co-primary efficacy endpoints, i.e. mean change from baseline in number of inflammatory lesions and percent of patients showing treatment success.

Based on these assumptions, 51 patients were to be enrolled in each treatment arm as shown in the tables below.

CCI			

The total sample size (153) was adjusted to 171 patients (57 in each treatment group) considering an expected dropout rate of about 10% (using Freedman's formula (Control Clin Trials, 1990): n'= 100*n/(100-x), where x is the expected dropout rate).

The initially planned sample size has been increased to a total of 201 patients (67 in each treatment group) to mitigate the impact on the statistical power of the treatment kit misallocation that occurred for 15 patients out of the initial 30 patients randomized. A cap of 33 subjects per arm having a negative L-BT result at screening (i.e., a test showing an increase \leq 10 ppm of H₂ by 90 minutes compared to time 0) is established.

Sample size for the sub-study on PK is not based on formal statistical assumptions. A cap of 12 subjects per arm is established. This is considered a good value for this kind of study. In any case, in order to have an adequate sample size, it is advisable to have at least 6 subjects per arm.

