16.3.1 Primary Efficacy Endpoints and Statistical Model of Analysis

Alfasigma S.p.A.

Study code: RE-ROS2002-2021

The co-primary efficacy endpoints, clinically assessed by the Investigator, are the absolute change from baseline in number of rosacea inflammatory lesions (papules and pustules) at the end of treatment AND the percent of subjects showing treatment success, defined as an IGA score of 0 (clear) or 1 (almost clear) with at least a 2-grade improvement from baseline at the end of treatment.

The first co-primary efficacy endpoint (i.e.: mean change from Baseline [V2] in number of inflammatory lesions at Day 30 [V3]) will be analysed by means of an Analysis of Covariance (ANCOVA) model, with change from Baseline to Day 30 as dependent variable, treatment group and stratification factor as explicative factors, and baseline number of inflammatory lesions as covariate. The adjusted mean differences will be presented with 95% CIs and p-values.

The second co-primary efficacy endpoint (i.e.: percent of patients showing treatment success) will be analysed by means of a stratified Cochran Mantel-Haenszel (CMH) chi square test. The Breslow-Day test for stratified tables will be applied. A two-sided 95% CI for difference in success rate between the treatment groups (each active group vs placebo) will also be computed.

All statistical tests will be conducted at the two-sided $\alpha = 0.05$ significance level. Due to the explorative purposes of this trial, no adjustment of significance level for multiplicity will be applied.

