16.3.2 Secondary Endpoints and Statistical Model of Analysis

16.3.2.1 Secondary Efficacy Endpoints and Statistical Model of Analysis

Exploratory secondary endpoints are the following:

- 1) Mean change from Baseline (V2) in number of inflammatory lesions (papules and pustules) at V4.
- 2) Percent of participants showing treatment success (i.e. IGA score of 0 or 1) at V3, V4.
- 3) Percent of participants with IGA score of 0 (clear) at V3, V4.
- 4) Change from Baseline (V2) in the following rosacea additional features at V3, V4:
 - pain, burning/stinging and itching (measured using a 0-10 cm Visual Analogue Scale (VAS))
 - telangiectasia (absent=0, mild=1, moderate=2, severe=3)
 - ocular manifestations (absent=0, mild=1, moderate=2, severe=3),
 - phymatous changes (absent=0, mild=1, moderate=2, severe=3).
- 5) Change from Baseline in facial non-transient erythema at V3, V4 (absent=0, mild=1, moderate=2, severe=3).
- 6) Change from baseline in abdominal pain score at V3, V4.
- 7) Change from baseline in abdominal distension score at V3, V4.
- 8) Change from baseline in bowel habit satisfaction score at V3, V4.
- 9) Change from baseline in global severity of abdominal symptoms score at V3, V4.
- 10) Percent of participants showing treatment success according to Modified IGA scale excluding papules/pustules but including erythema (i.e. score of 0 or 1) at V3, V4.
- 11) Percent of participant showing treatment success according to a Modified IGA scale including erythema and papules/pustules at V3 and V4.

The change from baseline to the relevant visit in secondary endpoints 1 and from 4 to 9 will be analyzed by means of an Analysis of Covariance (ANCOVA) Model, with change from Baseline to the relevant visit for the current endpoint as dependent variable, treatment group and stratification factor as explicative factors and baseline value of the current endpoint as covariate. The adjusted mean differences will be presented with 95% CIs and p-values.

The secondary endpoints expressed as percentages (endpoints 2, 3, 10 and 11) will be analyzed by means of a two-sided Cochran Mantel-Haenszel Chi-square test stratified by L-BT status. The Breslow-Day test for stratified tables will be applied. A two-sided 95% CI for difference of success rate between the treatment groups (each active group vs placebo) will also be computed.

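### SAP 4.3 names one randomisation factor where the protocol names two: check the IRT, align the SAP, and add PK participation to the ANCOVAs only if it was used

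*SAP*

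**What the plan says.** Protocol 10.3: "Patients will be stratified at randomization based on their L-BT status (negative vs. positive) and PK sub-study participation (yes or not"). Protocol 16 says the same of the list itself: "The randomization list will be stratified by L-BT status (negative vs positive) and by PK sub-study participation (yes or not"). The synopsis and sections 6 and 9.1 also give both factors.

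SAP 4.3: "Randomization will be stratified by the following factor", followed by L-BT H2 at or below 10 ppm and above 10 ppm, and nothing else. Yet SAP 4.1 randomises consenting PK patients within their stratum, and SAP 5.4.7 defines the PK set through sub-study strata. SAP Section 10 lists three changes to the protocol: the use of the analysis populations, the PK set definition and the added subgroups. Dropping a randomisation factor is not among them.

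For the models, Protocol 16.3.1 has "treatment group and stratification factor as explicative factors, and baseline number of inflammatory lesions as covariate", with the factor in the singular and unnamed. SAP 7.2, 7.3.1 and 7.3.4 to 7.3.6 use L-BT status. For secondary binary endpoints Protocol 16.3.2.1 has a "Cochran Mantel-Haenszel Chi-square test stratified by L-BT status", and SAP 7.1 applies the same to all binary efficacy endpoints.

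The protocol describes entry to the sub-study in two ways. The synopsis says "Patients participating in the PK study will be randomly" selected; section 10.3 says "The subjects will be offered participation to the PK sub-study".

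**The concern.** The two documents describe different randomisations, and the SAP also disagrees with itself. If 4.3 is right, the strata in 4.1 and 5.4.7 do not exist; if those sections are right, 4.3 is incomplete.

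Two things depend on the answer. First, SAP 6.3 counts mis-stratification as a protocol deviation, and SAP 5.4.6 analyses wrongly stratified patients by their actual stratum. Neither rule can be applied to PK status until the factors are known. Second, a model should normally reflect the factors used to allocate. If PK participation was balanced by design and predicts lesion change, an ANCOVA without it leaves that variation in the residual and reports a standard error that is too large. Allocation in this trial already needs careful documentation, given the "treatment kit misallocation that occurred for 15 patients out of the initial 30 patients randomized".

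**Working it through.** **Sample size used.** The plan's figure reproduces: 51/(1 − 0.10) = 56.7, rounded up to 57 per arm; 3 × 57 = 171; 171 + 30 = 201 = 3 × 67. The step to 51 cannot be checked because its inputs are redacted.

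**Inputs.** 67 per arm. PK patients: 12 per arm (36 in all, Protocol 16.1 cap) or 19 per arm (57 in all, raised cap in SAP 4.5). L-BT negative: 33 per arm, assumed at the cap. PK effect on lesion change: d residual SD, assumed 0 to 0.6, because the documents give no value.

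**Analytic check, PK-stratified allocation.** With a fraction p of PK patients in each arm, leaving the term out multiplies the residual variance by 1 + p(1 − p)d². The interval is therefore too wide by √(1 + p(1 − p)d²) − 1.

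- p = 12/67 = 0.179, p(1 − p) = 0.147: 0.29%, 1.17% and 2.61% at d = 0.2, 0.4 and 0.6.
- p = 19/67 = 0.284, p(1 − p) = 0.203: 0.41%, 1.61% and 3.59%.

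**Simulation of the pairwise ANCOVA in SAP 7.2** (treatment, L-BT, baseline; with or without PK). Entries are the excess CI width without the PK term; a negative value means the interval is wider with the term.

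| Case | PK patients | d = 0 | 0.2 | 0.4 | 0.6 |
|---|---|---|---|---|---|
| (a) PK-stratified, as randomised | 36 | −0.01% | 0.29% | 1.19% | 2.65% |
| | 57 | −0.01% | 0.40% | 1.65% | 3.66% |
| (b) as (a), by treatment received | 36 | −0.09% | 0.21% | 1.09% | 2.57% |
| | 57 | −0.09% | 0.32% | 1.56% | 3.56% |
| (c) L-BT-stratified only | 36 | −0.39% | −0.09% | 0.78% | 2.23% |
| | 57 | −0.40% | 0.02% | 1.22% | 3.23% |

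Cases (a) and (c) used 100,000 runs and (b) 60,000. Case (b) moves 15 of the first 30 patients to another arm at random. That pattern is assumed, and the case is closest to the planned primary analysis by actual treatment.

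**Reported error against true error, case (a), d = 0.6.** The true SD of the estimate without/with the term is 0.1730/0.1730 (36) and 0.1739/0.1738 (57). The mean reported SE is 0.1777/0.1731 and 0.1794/0.1731. Only the reported error is affected.

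**Type I error.** Rejection under the null at nominal 0.05 runs from 0.043 to 0.052 over all cases.

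**Second simulation** (5,000 runs per scenario, blocks of 6 assumed, both factors used to allocate). At d = 0.5, ANCOVA type I error without/with the term was 4.7%/5.2% (36) and 4.1%/4.9% (57). Power for an assumed 0.5 SD treatment difference was 86.3%/87.3% and 86.6%/87.8%. At d = 0 the differences were at most about 0.1 point. For the CMH test, type I error was 4.5 to 5.4% stratified by L-BT and 4.6 to 5.6% by L-BT × PK, with power within 1 point. Simulation error is about 0.3 points for type I error and 0.5 to 0.6 points for power.

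**The case against.** The strongest reply is that this is a wording slip and the ANCOVA change is a preference. The protocol's five statements, together with SAP 4.1 and 5.4.7, all point to PK strata, so an omission in 4.3 is the likelier reading. The analysis factor is consistently L-BT: SAP 5.7.1 names it so, and the protocol's model text uses the singular. Protocol 10.3 presents the PK stratum as a way to keep the sub-study balanced, not as a prognostic factor. The loss is conservative, small and conditional on an undocumented effect, and the secondary results are to be read descriptively.

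Much of this stands. Omitting PK from the SAP models does not depart from the protocol's model text, and the point is minor. It does not remove the contradiction, which only the IRT specification can settle. If PK was a stratum, the term costs about 0.01% in width analysed as randomised and about 0.1% by treatment received.

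A second reply is that tying the term to the IRT is not what the figures favour: in case (c) the term also helps once d exceeds about 0.2. That is correct. The rule rests on the convention that analysis follows randomisation. If PK was not a stratum, it is an ordinary covariate with no evidence of prognostic value and a cost of about 0.4% at zero effect, so there is no good reason to change the pre-specified model.

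**Conclusion.** The contradiction is certain and rests on no assumption: two factors in the protocol, one in SAP 4.3, and no declaration in SAP Section 10. Its statistical effect is small. If the IRT stratified by PK participation, the reported intervals without the term are 0.3 to 2.6% (36 patients) or 0.4 to 3.7% (57) too wide analysed as randomised, and 0.2 to 2.6% or 0.3 to 3.6% by treatment received. These ranges assume a PK effect of 0.2 to 0.6 SD, 33 L-BT negative patients per arm and, for treatment received, a random switch pattern. There is no bias, no type I error inflation and no loss in the true precision of the estimate. With no PK effect there is no gain. The correction is worth making because it is nearly free; it does not threaten the primary result.

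**What to change.** 1. Check the IRT specification for the factors actually used, and make SAP 4.1, 4.3 and 5.4.7 agree with it.
2. If PK participation was used: list both factors with their levels in SAP 4.3, add PK participation (yes, no) as a factor in the ANCOVAs of SAP 7.2, 7.3.1 and 7.3.4 to 7.3.6, and declare the addition in Section 10.
3. If only L-BT was used: declare the departure from Protocol 10.3 and 16 in Section 10, correct the reference to PK strata in 5.4.7, and leave the models unchanged.
4. In both cases keep the CMH and Breslow-Day tests stratified by L-BT, and say so. Each PK × L-BT cell would hold only about 6 to 10 patients per arm (12 × 33/67 = 5.9; 19 × 34/67 = 9.6), and the finer stratification changed the CMH results little.

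The cost is one IRT check, a few lines of SAP text and, if PK was used, one degree of freedom per ANCOVA. No new data are needed. A change to the primary model would need an SAP amendment under SAP Section 2, made before database lock and unblinding.
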